10.4. Statistical methods

For the primary estimand of the primary endpoint, a linear mixed model (LMM) with subject-specific random intercept will be specified to assess possibles changes over time within and among groups. LMM accounts for both fixed and random effects, can analyze data with repeated measures as well as can handle missing values. Specifically, the LMM will include treatment, time, and time*treatment interaction term as fixed effects, and subject/participant as a random effect. An unstructured correlation matrix will be used. Missing values will be imputed as part of the LMM model assumptions.

No adjustments will be made for multiplicity.

For continuous variables, differences in mean or median between groups will be assessed using Student's t-test (parametric) or Mann-Whitney test (non-parametric) depending on the

 Version No:

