4.2. Description of Objectives, Endpoints and Estimands

The primary, secondary and tertiary/exploratory objectives and endpoints assessed (as described in the schedule of activity) to assess the effect of oral Administration of nirmatrelvir/ritonavir in patients with post-COVID-19 symptoms are summarized in the table below.

Objectives	Endpoints	Estimand
Primary	Primary	Primary
To evaluate the effect of oral administration of nirmatrelvir/ritonavir at Day 16 on quality of life	Change from baseline on the EQ-5D-5L VAS scale at day 16	Estimand 1: This estimand is intended to provide a population-level estimate of the mean treatment effect (nirmatrelvir/ritonavir relative to placebo) on a continuous endpoint over time for all randomized/evaluable participants. The difference of Day 16 on EQ-5D-5L VAS scale between the nirmatrelvir/ritonavir and placebo arms in participants with long COVID estimated with a longitudinal analysis that controls for baseline assessment
Secondary	Secondary	Secondary
To evaluate the effect of oral administration of nirmatrelvir/ritonavir in patients with post-COVID-19 symptoms over time on quality of life	Change from baseline on the EQ-5D-5L VAS scale at day 45 and on Day 90	Estimand 1 (see above)

 Version No:

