 2.0 Final

 Date:
 10 March 2023

 EudraCT No:
 2022-003855-32

	T	
To evaluate the effect of oral administration of nirmatrelvir/ritonavir on hemodynamic response (only patients diagnosed with POTS)	Change from baseline over time as measured in delta maximum heart rate during active standing test	Estimand 1 (see above)
To evaluate the effect of oral administration of nirmatrelvir/ritonavir on fever MAPS (only patients diagnosed with POTS)	Change from baseline over time in POTS-specific symptoms as measured by MAPS	Estimand 1 (see above)
To evaluate the effect of oral administration of nirmatrelvir/ritonavir on reactive hyperemia index	Change from baseline endothelial function measured by the EndoPat® device on Day 45	Estimand 2: This estimand is intended to provide a population-level estimate of the mean treatment effect (nirmatrelvir/ritonavir relative to placebo/ritonavir) on a continuous endpoint at a given time point for all randomized/evaluable participants. The difference of Day 45 on endothelial function test between the nirmatrelvir/ritonavir and placebo/ritonavir arms in participants with long COVID estimated with an ANCOVA model that controls for baseline assessment
To evaluate the effect of oral administration of nirmatrelvir/ritonavir in 24-h average heart rate	Change from baseline over time in heart rate by ECG monitoring device	Estimand 1 (see above)
To evaluate the effect of oral administration of nirmatrelvir/ritonavir fever	Change from baseline over time in body temperature	Estimand 1 (see above)
To evaluate the effect of oral administration of nirmatrelvir/ritonavir on physical capacity	Change from baseline over time as measured by 6- minute walk test	Estimand 1 (see above)

 Version No:

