10.1. Estimands

10.1.1. Primary estimand

• For a given endpoint, the primary estimand will be the population average treatment effect on the change from baseline over time of nirmatrelvir/ritonavir compared to placebo/ritonavir. Measurements after discontinuation of study intervention will be censored and treated as missing data. Missing data due to censoring, study withdrawal or other reasons (e.g., laboratory failure) will have data imputed based on a missing at random (MAR) assumption. Participants with inadequate compliance will have their values used as-is in the analysis. The population-based treatment effect will be the difference in the mean change from baseline in nirmatrelvir/ritonavir arm compared to placebo/ritonavir.

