 2.0 Final

 Date:
 10 March 2023

 EudraCT No:
 2022-003855-32

fulfillment of the distributional assumptions of approximation for a normal distribution (Kolmogorov-Smirnov test). Differences in mean or median within groups at Days 16, 45 and 90 with respect to baseline, will be assessed using paired Student's t-test (parametric) or Wilcoxon's signed-rank test (non-parametric) as appropriate.

For continuous primary estimands of secondary endpoints, analysis of covariance (ANCOVA) will be performed to assess changes from baseline on Days 16, or Day 90. Specifically, the ANCOVA will include treatment as fixed effects, and baseline as a covariate.

For dichotomous variables, change in proportions within groups at Days 16, 45 and 90 with respect to baseline (pre-treatment vs post-treatment) will be assessed using McNemar's test.

For categorical variables, frequency distributions will be estimated and compared between the groups using Chi-squared test or the exact Fisher test.

With all baseline demographic and patient's medical history variables a logistic regression model will be adjusted for studying the influence of each of them in the response to treatment. No values will be imputed for missing data, and missing values will not be included in the model.

Sensitivity analyses will be detailed in the SAP prior to database lock and may be include analyses described in the a forementioned alternative study populations.

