10.5. Sample size calculations

The statistical power to detect a 10-unit placebo/ritonavir adjusted improvement from baseline to Day16 (primary endpoint) was estimated using the following assumptions: a 2:1 case-control ratio, nominal significance of alpha=0.05, 1-tailed test and 90 % power. Based on these assumptions, the study population would need to be at least 207 patients. In the study, ~400 participants will be randomized to a) have at least 207 completers to account for 48% dropouts during the execution of the study and b) increase the statistical power for the secondary endpoints of the study that will only be measured in the subset of patients with POTS, and for the secondary endpoints for which the variabilities in the Swedish post-covid patient population are not well documented.

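### Section 4.2 says the primary Day 16 VAS analysis controls for baseline, but the mixed model in Section 10.4 lists no baseline term and does not state its response variable

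*Protocol*

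**What the plan says.** In the table of Section 4.2, Estimand 1 covers the primary endpoint, change from baseline in EQ-5D-5L VAS at Day 16. The difference between arms is to be "estimated with a longitudinal analysis that controls for baseline assessment". Estimand 2 in the same table uses the same phrase for a single-time-point analysis: "estimated with an ANCOVA model that controls for baseline assessment".

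Section 10.4 specifies a linear mixed model with a subject-specific random intercept for the primary endpoint, "to assess possibles changes over time within and among groups". It then lists the terms: "the LMM will include treatment, time, and time*treatment interaction term as fixed effects, and subject/participant as a random effect". No baseline term appears, and neither the response variable nor the levels of time are stated. For the secondary ANCOVA the same section does write baseline out: "the ANCOVA will include treatment as fixed effects, and baseline as a covariate".

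Two other places bear on the point. Section 10.1.1 says "Measurements after discontinuation of study intervention will be censored and treated as missing data", with missing values handled under missing at random (MAR). Section 10.5 gives the design figures, "nominal significance of alpha=0.05, 1-tailed test and 90 % power" for a 10-unit difference with 2:1 allocation, and randomises about 400 to "have at least 207 completers to account for 48% dropouts during the execution of the study".

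**The concern.** The protocol fixes the terms of its primary model, and they do not match its own description of the estimator. In Sections 4.2 and 10.4 taken together, controlling for baseline means a baseline covariate where the ANCOVA is concerned. The primary model has none.

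Three analyses remain open: a change-score response without baseline, a model with baseline as one of the repeated responses, and a model with a baseline covariate. The first two coincide with complete data; the third does not. An adjusted and an unadjusted analysis give different Day 16 estimates and p-values whenever the arms differ by chance at baseline. The first two also part company once data are missing. The choice should be settled before unblinding. Also at stake is some precision that costs nothing, because baseline VAS is already scheduled for every patient.

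**Working it through.** **1. The protocol's own figure.** Section 10.5 states no SD, so 207 can only be inverted. With 138 versus 69, a difference of 10, one-tailed alpha 0.05 and 90% power:

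SD of change = 10 × √(69/1.5) / (1.645 + 1.282) = 23.2 (normal approximation), or 23.1 from the noncentral t.

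The dropout inflation agrees with the text: 207 / (1 − 0.48) = 398.1, rounded up to 399, about 400.

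**2. What the listed terms estimate.** If the response is change, treatment by time without baseline gives the difference in mean change at Day 16. If baseline is a level of time, the Day 16 interaction contrast is again the difference in mean change. A numerical generalised least squares check on balanced complete data gave −3.0667 for the interaction contrast and −3.0667 for the simple change-score difference. Neither coding adjusts for baseline in the covariate sense.

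**3. Size of the discrepancy in the estimate.** Let s0 and s1 be the SDs at baseline and Day 16, and ρ their correlation. The adjusted estimate minus the change estimate is (1 − β) × the baseline difference between arms, with β = ρ·s1/s0. As an illustration, take s0 = 14.4 (uniform on 0 to 50, in line with entry at VAS below 50) and ρ = 0.3. Then s1 = 22.9 (formula in step 4) and β = 0.3 × 22.9/14.4 = 0.48. One standard error of chance imbalance is 14.4 × √(1/138 + 1/69) = 2.1 points, so the two analyses differ by 0.52 × 2.1 = 1.1 points. The standard error of the change contrast is 23.1 × √(1/138 + 1/69) = 3.4.

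**4. Precision.** For assumed s0 and ρ, s1 solves s1² + s0² − 2ρ·s0·s1 = 23.1², so s1 = ρ·s0 + √(23.1² − s0²(1 − ρ²)). The variance ratio, adjusted over unadjusted, is (1 − ρ²)·s1² / 23.1². With q = s0/s1 this equals (1 − ρ²)/(1 + q² − 2ρq). Denominator minus numerator is (q − ρ)², so the ratio never exceeds 1. Power is one-tailed from the noncentral t with 204 df and SD 23.1 × √ratio.

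| Baseline SD | ρ | s1 | Variance ratio | Power at 207 |
|---|---|---|---|---|
| none (unadjusted) | – | – | 1 | 90.0% |
| 10 | 0.4 | 25.2 | 1.00 | 90.0% |
| 12 | 0.5 | 26.6 | 1.00 | 90.1% |
| 12 | 0.7 | 29.9 | 0.85 | 93.6% |
| 14.4 | 0.3 | 22.9 | 0.89 | 92.7% |
| 16 | 0.3 | 22.1 | 0.84 | 94.0% |
| 8 | 0.7 | 28.0 | 0.75 | 95.9% |
| 16 | 0.2 | 20.2 | 0.73 | 96.2% |

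The last two rows are the largest gains for baseline SDs of 8 to 16 and correlations of 0.2 to 0.7. With all 400 evaluable, unadjusted power is 99.2% and the gain is under 1 point throughout.

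**5. Missing data.** If the response is change and baseline is omitted, the bias is (ρ·s1 − s0) × the between-arm difference in mean standardised baseline among those observed. Suppose, purely as an assumption, that 20% per arm are missing at Day 16 and that the log-odds of dropout rise by 0.5 per baseline SD in one arm only. The observed means then differ by 0.096 SD. Over the same range, ρ·s1 − s0 runs from 0.2 × 20.2 − 16 = −12.0 to 0.7 × 28.0 − 8 = 11.6. Multiplied by 0.096, the bias is about 1.1 points in either direction, against a true effect of 10.

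In simulations with a deliberately extreme 48% lost before Day 16 (baseline SD 12 to 16, ρ 0.3 to 0.7), the change-only mean ran from 8.03 to 12.06. The baseline-adjusted mean ran from 9.85 to 10.12, and the model with baseline as a response from 9.82 to 10.15. With the same dependence in both arms, the change-only mean was 9.88 to 10.10.

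**The case against.** The best defence is that baseline may be meant as a level of time. The aim of assessing changes within and among groups fits that reading, and Section 10.1.1 defines the effect as the difference in mean change from baseline. The interaction then handles baseline through the change, and the model uses every patient's baseline and stays valid under MAR. An ANCOVA can use baseline only as a covariate, so the parallel with Estimand 2 is an analogy and not proof. Section 10 also defers further detail to a SAP. This stands in part: the coding is plausible and is a weaker form of baseline control. But Section 10.4 does not state it, a change-score response is equally open, and with complete data neither coding delivers the adjustment that Section 4.2 appears to promise.

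A reader might infer that the primary analysis is invalid or underpowered. The documents do not support that: the contrast is unbiased under randomisation with complete data, and power does not fall below the planned 90%.

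A reader might also infer that 48% dropout biases the primary result. That does not follow. The 48% covers the whole study to Day 90 and not the time to Day 16, and Section 10.5 gives a second reason for randomising 400. Bias needs a change-score response, an omitted baseline, and dropout that depends on baseline differently by arm. A model that honours Section 4.2 would not omit baseline.

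Finally, the power gain is not a figure of the protocol. Equal SDs at both visits with ρ = 0.3 would give 7.6 points, but imply a baseline SD of 19.5, hard to square with entry below 50. Eligibility is set at screening, so the Day −1 spread could be somewhat wider than the entry limit suggests.

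**Conclusion.** The point holds as a mismatch between Sections 4.2 and 10.4 that leaves the primary estimator open, not as a fault that invalidates the trial. That much rests on the text alone.

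The size rests on assumptions. With an SD of change of 23.1 (implied by 207, not stated), baseline SDs of 8 to 16 and correlations of 0.2 to 0.7, adjustment raises power at 207 completers by anything from nothing to about 6 points. With 400 evaluable it adds less than 1. Adjustment for baseline is therefore a free improvement and not a rescue of the design.

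The missing-data argument is secondary and conditional on the change-score coding. Under MAR, a baseline covariate or baseline as a response level removes it.

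**What to change.** In Section 10.4, state the response variable and the levels of time for the primary model. Then choose one of two forms:

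- VAS at the post-baseline visits (or change from baseline) as the response, with baseline VAS and baseline-by-visit added to treatment, time and their interaction as fixed effects; or
- baseline kept as a level of time, with baseline means constrained equal across arms.

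In either form, name the Day 16 difference between arms as the primary contrast, as Section 4.2 and the hypotheses in Section 10 already do. Any SAP should repeat the same form.

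The cost is a few lines of text before unblinding. No new data, visits or patients are needed.

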 2.0 Final

 Date:
 10 March 2023

 EudraCT No:
 2022-003855-32

fulfillment of the distributional assumptions of approximation for a normal distribution (Kolmogorov-Smirnov test). Differences in mean or median within groups at Days 16, 45 and 90 with respect to baseline, will be assessed using paired Student's t-test (parametric) or Wilcoxon's signed-rank test (non-parametric) as appropriate.

For continuous primary estimands of secondary endpoints, analysis of covariance (ANCOVA) will be performed to assess changes from baseline on Days 16, or Day 90. Specifically, the ANCOVA will include treatment as fixed effects, and baseline as a covariate.

For dichotomous variables, change in proportions within groups at Days 16, 45 and 90 with respect to baseline (pre-treatment vs post-treatment) will be assessed using McNemar's test.

For categorical variables, frequency distributions will be estimated and compared between the groups using Chi-squared test or the exact Fisher test.

With all baseline demographic and patient's medical history variables a logistic regression model will be adjusted for studying the influence of each of them in the response to treatment. No values will be imputed for missing data, and missing values will not be included in the model.

Sensitivity analyses will be detailed in the SAP prior to database lock and may be include analyses described in the a forementioned alternative study populations.

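### Section 10.4 adds an unadjusted comparison, chosen by a normality pre-test, beside the LMM and ANCOVA, so an endpoint can carry a second p-value for a different quantity

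*Protocol*

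**What the plan says.** Section 10.4 of the protocol names three between-arm analyses for continuous data.

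- **Primary endpoint:** "For the primary estimand of the primary endpoint, a linear mixed model (LMM) with subject-specific random intercept will be specified". Its terms are listed: "the LMM will include treatment, time, and time*treatment interaction term as fixed effects, and subject/participant as a random effect".
- **Secondary endpoints:** "For continuous primary estimands of secondary endpoints, analysis of covariance (ANCOVA) will be performed to assess changes from baseline on Days 16, or Day 90", and "the ANCOVA will include treatment as fixed effects, and baseline as a covariate".
- **Continuous variables in general:** "For continuous variables, differences in mean or median between groups will be assessed using Student's t-test (parametric) or Mann-Whitney test (non-parametric) depending on the" "fulfillment of the distributional assumptions of approximation for a normal distribution (Kolmogorov-Smirnov test"). This third rule names no endpoint, visit or covariate.

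The sentence after the third rule applies the same parametric or non-parametric choice to within-arm changes at Days 16, 45 and 90. Section 10.4 also says that multiplicity is not adjusted for.

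The target of estimation is set elsewhere. Section 10.1.1 states: "The population-based treatment effect will be the difference in the mean change from baseline" between the arms, and Section 10.1.2 uses the same summary. The table in Section 4.2 defines Estimands 1 and 2 as mean treatment effects from analyses that control for the baseline assessment.

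**The concern.** The third rule sits in the methods section, not in Section 10.3 (Descriptive), and it is not limited to baseline characteristics. Its companion sentence on Days 16, 45 and 90 shows that outcomes are in view. On its face it therefore covers the same continuous endpoints as the LMM and ANCOVA.

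Three things follow. First, the hypothesis tested is chosen by the trial data: a difference in means if normality is not rejected, a rank comparison if it is. Second, neither branch uses baseline as a covariate. Third, the reader may face two p-values per endpoint, one from the model and one from the data-selected test. The protocol has many secondary endpoints and no multiplicity adjustment, so that leaves room to report whichever result is more favourable.

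**Working it through.** **1. Target of each analysis**

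| Analysis | Quantity compared | Baseline as covariate | Chosen by pre-test |
|---|---|---|---|
| Estimands (4.2, 10.1) | difference in mean change | control required | – |
| LMM (10.4) | mean difference | none in the listed terms | no |
| ANCOVA (10.4) | mean difference | yes | no |
| Student's t-test (10.4) | mean difference | no | yes |
| Mann-Whitney (10.4) | rank comparison; in general neither a mean nor a median difference | no | yes |

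The protocol says "differences in mean or median between groups will be assessed using" one of the last two. Only one of those two addresses the estimand's summary measure, and neither adjusts for baseline. A t-test on change does use baseline, by subtraction, but inefficiently.

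**2. How the pre-test behaves**

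These are simulations on assumed distributions, with a 5% Kolmogorov-Smirnov test on pooled within-arm residuals. The 207 patients of Section 10.5 at 2:1 are 138 vs 69. The smaller case, 40 vs 20, stands for the POTS-only endpoints: Section 2.1 reports POTS in 25–30% of patients, and 0.25 × 207 = 52 to 0.30 × 207 = 62. That the trial has the same share is an assumption.

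| Data | Patients | Mann-Whitney chosen, standard KS | Mann-Whitney chosen, Lilliefors |
|---|---|---|---|
| Normal | 138 vs 69 | about 0% | 6% |
| t with 5 df | 138 vs 69 | 7% | 57% |
| Lognormal, log-SD 0.5 | 138 vs 69 | 90% | 100% |
| Lognormal, log-SD 0.5 | 40 vs 20 | 15% | 74% |

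The same distribution leads to different tests at different sample sizes. The pre-test therefore does not track whether a comparison of means is valid.

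**3. Error rate of the two-stage procedure** (138 vs 69, two-sided 5%, standard KS)

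- Same distribution in both arms: 4.7% (normal) and 5.1% (skewed). The level is kept.
- Equal means, skewed data, control SD 1.5 times larger: 18% rejections, against 4% for a Welch test. With equal means these are not evidence of a mean difference; the Mann-Whitney branch is answering another question.

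**4. Precision of the competing test**

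The protocol's figure comes first. Section 10.5 gives 10 units, one-sided 0.05, 90% power, 2:1 and 207 patients, but no SD. Solving for it:

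SD = 10 / [(1.645 + 1.282) × √(1/138 + 1/69)] = 10 / (2.926 × 0.1474) = 23.2.

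The dropout step also reproduces: 207 / (1 − 0.48) rounds up to 399, against about 400.

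Take 23.2 as the SD of change. The variance of the change-score comparison relative to ANCOVA is 2/(1 + r), where r is the correlation between baseline and follow-up. The documents give no r.

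- t-test on change: Φ(2.926 − 1.645) = 90%.
- ANCOVA, r = 0.4: ratio 2/1.4 = 1.43; Φ(2.926 × √1.43 − 1.645) = Φ(1.85) = 97%.
- ANCOVA, r = 0.2: ratio 1.67; Φ(2.13) = 98%. At r = 0.7: ratio 1.18; Φ(1.53) = 94%.

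If instead ANCOVA is the analysis with 90% power at 207, the change-score t-test has 73% at r = 0.2, 76% at 0.3, 81% at 0.5 and 85% at 0.7. With all 400 patients (267 vs 133) and SD 23.2, both tests exceed 99%.

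**The case against.** The strongest reply is that the wording already implies an order. The LMM and ANCOVA are tied by name to the estimands; the t-test and Mann-Whitney are tied to none and stand in a run of generic sentences on continuous, dichotomous and categorical variables. On that reading they are supplementary. Section 10 also says that the SAP gives further detail, and the version of the Kolmogorov-Smirnov test and any transformations are ordinary SAP content.

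Much of this stands, and it rules out several stronger readings. A reader might infer that the pre-test selects the primary analysis or that baseline information is discarded. The documents do not support that: no pre-test governs the LMM or ANCOVA, and the ANCOVA has baseline as a covariate. A reader might infer that the trial loses power; a supplementary test takes none from the named models. Nor is the two-stage test shown to inflate error in general: it keeps its level when the arms share a distribution, and the 18% needs assumed skew together with unequal SDs. The unnamed test version is not an error in a protocol.

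The reply does not remove the rule. It is stated, not merely left open; it sits among the inferential methods; nothing marks it as descriptive; and its Mann-Whitney branch has a different target from the estimands.

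**Conclusion.** The point holds in a limited form. Section 10.4 sets an unadjusted between-arm comparison, selected by a normality pre-test, beside the named models, without limiting which variables it covers. In the Mann-Whitney branch it does not address the difference in mean change, and in neither branch does it meet the baseline control of Section 4.2. The main consequence is two competing answers for the same endpoint without multiplicity adjustment.

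The lower precision belongs to the competing test alone: about 90% against 97% at the protocol's own effect size and alpha. This rests on an SD back-solved from 207 and taken as the SD of change, and on an assumed r of 0.4; for r from 0.2 to 0.7, ANCOVA has 98% to 94%. The figures on how often each branch is chosen rest on assumed distributions and show the direction of the problem, not its size in this trial.

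**What to change.** In Section 10.4:

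- Delete the Kolmogorov-Smirnov rule and the t-test/Mann-Whitney comparison for efficacy endpoints, or label that comparison descriptive only.
- State that the baseline-adjusted LMM or ANCOVA is the only inferential between-arm analysis for each continuous endpoint, whatever a normality test shows. The listed LMM terms name no baseline covariate, so the sentence should also say how baseline enters that model.
- Fix in advance any transformation of skewed biomarkers (CRP, D-dimer, ferritin and NT-proBNP are candidates) and any rank-based sensitivity analysis. The details can go in the SAP, but a pre-test should not choose them.

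The cost is a change of wording. No data collection or sample size changes, and fewer analyses are run.

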2.1. Post-acute COVID-19 syndrome (PACS) and Postural orthostatic tachycardia syndrome (POTS)

Hospitalized patients with severe COVID-19 generally show rapid improvement of the widespread radiological abnormalities seen during the acute phase of COVID-19 pneumonia. However, at six-month follow-up in patients hospitalized för COVID-19 "fibrotic-like" changes have been reported on chest CT. Caruso et al [1] found that 72% of the study participants had signs of "fibrotic-like" changes, whereas only 35% was seen in the study by Han et al [2]. Within the UPPCOV and RECOV research projects [3] of patients with long COVID, many hospitalized patients exhibit residual fibrotic changes as well as bronchiectasis (manuscript in preparation). Restrictive lung function impairment and reduced diffusion capacity is relatively common with prolonged oxygen dependency over time in the most advanced cases. A common finding in the hospitalized patient cohort, and to a lesser extent also in the non-hospitalized cohort, is an uneven parenchymal attenuation in expiratory images with high-resolution computer tomography (HRCT).

Non-hospitalized patients with severe PACS often exhibit dysfunctional breathing patterns with or without hyperventilation triggered by mild/moderate mental and/or physical effort. The level of activity necessary to provoke this abnormal breathing is generally very modest. Moreover, the degree of symptoms varies over time without any obvious triggers. Studies regarding correlation with respiratory symptoms and physiological function as well the pathophysiological mechanism are ongoing as well as rehabilitative interventions. Another frequent objective disease manifestation is post-COVID POTS, which has within our UPPCOV and RECOV research projects mainly been seen in non-hospitalized patients (currently ~200 patients, or 25-30%) (unpublished observation). Unlike classical POTS patients, post-COVID POTS patients often have dyspnea with desaturation upon walking and pulmonary changes (mosaic pattern) in expiratory HRCT imaging suggestive of an overlap among multiple phenotypes. Also, other cardiovascular manifestations e.g., microvascular dysfunction and inappropriate sinus tachycardia, have been diagnosed predominantly in the non-hospitalized cohort.

Fatigue, post-exertional malaise, brain fog, cognitive impairment and breathlessness are common symptoms across all phenotypes and are also commonly reported symptoms reported in other studies [4].

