 2.0 Final

 Date:
 10 March 2023

[figure not shown]
 EudraCT No:
 2022-003855-32

A total of 400 patients with post-COVID conditions will be enrolled in this study. Patients will be randomized in a ratio of 2:1 to receive either nirmatrelvir/ritonavir or placebo/ritonavir. For details, see Section 7, Study treatments.

The planned length of participation in the study for each patient is a maximum of 90 days, with potential for long-term clinical follow-up at 6 and 12 months through Electronic Medical Records and national registries. The study consists of a maximum of five visits.

The study design is outlined in Figure 1 and the planned schedule of assessments at each visit are detailed in Table 1.

Figure 1 Study design

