6.2. Inclusion criteria

To be included in the study, subjects must meet the following criteria:

- 1. The subject has given written consent to participate in the study.
- 2. ≥18 years of age at the time of the Screening Visit
- 3. Post-acute COVID-19 syndrome (PACS) according to the WHO definition
- 4. EQ-5D-5L VAS< 50

 Version No:

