6.4. Screening

Subject eligibility (that subjects fulfill all inclusion criteria and do not meet any exclusion criteria) is established at the screening visit before randomization.

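### Unadjusted within-arm tests against baseline, not labelled descriptive, can be significant without a drug effect, and for a moderate common shift more often in the arm that is twice as large

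*Protocol*

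**What the plan says.** Section 10.4 (Statistical methods) tests each arm against its own baseline. For continuous variables the comparison is "Differences in mean or median within groups at Days 16, 45 and 90 with respect to baseline"; the methods named are the paired t-test and, as the non-parametric alternative, the Wilcoxon test. For dichotomous variables, "change in proportions within groups at Days 16, 45 and 90 with respect to baseline" is tested with McNemar's test. The same section rules out multiplicity adjustment. It gives the within-arm tests no supportive or descriptive status, although section 10.3 is reserved for descriptive statistics.

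The trial's question is a comparison between arms. The hypotheses in section 10, the estimands in sections 4.2 and 10.1, and the mixed model in section 10.4 all contrast nirmatrelvir/ritonavir with placebo/ritonavir. The primary endpoint is "Change from baseline on the EQ-5D-5L VAS scale at day 16".

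Three design features bear on the within-arm tests:
- Entry requires "EQ-5D-5L VAS< 50" (section 6.2), which is the scale of the primary endpoint.
- Eligibility "is established at the screening visit before randomization" (section 6.4). Table 1 then measures EQ-5D-5L again at the Day -1 baseline visit.
- "Patients will be randomized in a ratio of 2:1 to receive either nirmatrelvir/ritonavir or placebo/ritonavir" (section 5.1).

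**The concern.** A paired test against baseline asks whether patients in one arm changed, not whether the drug changed them. A placebo response on a self-rated scale, the natural course of the illness, and any regression to the mean left after entry below 50 would move both arms alike. Each can produce a small p-value with no drug effect.

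Unequal allocation adds a second problem. For the same true change, the larger arm has the smaller standard error and so crosses the significance threshold more often. A report that follows section 10.4 could therefore state that the active arm improved significantly and the control arm did not, when the contrast reflects sample size only. The tests apply at three visits and, as worded, to continuous variables in general, without adjustment. A neutral primary result could thus be accompanied by apparently favourable supportive statements.

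**Working it through.** **Inputs from the protocol.** Section 10.5 gives 10 units, 2:1 allocation, one-sided alpha 0.05, 90% power, 207 patients and 48% dropout. It gives no SD, and no section gives a retest correlation or an expected control-arm change.

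**The plan's own figure.** With 2:1 allocation the control-arm size is 1.5 × (1.645 + 1.282)² × SD² / 10² = 0.1285 × SD². Setting this to 69 (207 / 3) gives SD² ≈ 537, so SD ≈ 23.2. Rounding each arm up, SD 23 gives 204 in total and SD 23.2 gives 210, both close to 207. The dropout step reproduces: 207 / (1 − 0.48) = 398, or about 400. The SD of 23.2 is therefore implied, not stated. I use it as the SD of change.

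**Within-arm tests with no drug effect.** Assume a paired t-test at two-sided 0.05, significant in the direction of improvement, and the same mean shift d in both arms. The normal approximation is P = Φ(d / (SD/√n) − 1.96). At d = 4 with everyone randomised:
- n = 267: SE = 23.2/√267 = 1.42; 4/1.42 − 1.96 = 0.86; P = 0.80.
- n = 133: SE = 23.2/√133 = 2.01; 4/2.01 − 1.96 = 0.03; P = 0.51.
- Active significant and control not: 0.80 × (1 − 0.51) = 0.39. The reverse: 0.51 × (1 − 0.80) = 0.10.

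With the planned completers (138 and 69) and the noncentral t distribution:

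| Common shift (points) | Control significant | Active significant | Active only | Control only |
|---|---|---|---|---|
| 0 | 2.5% | 2.5% | 2.4% | 2.4% |
| 2 | 10.5% | 17.0% | 15% | 9% |
| 3 | 18% | 33% | 27% | 12% |
| 4 | 29% | 52% | 37% | 14% |
| 5 | 42% | 71% | 41% | 12% |
| 8 | 81% | 98% | 19% | 2% |
| 10 | 94% | 99.9% | 6% | 0.1% |

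The last two columns are products for independent arms. At 4 points, for example, 0.52 × (1 − 0.29) ≈ 0.37. The asymmetry is nil at zero shift, largest at about 4 to 5 points, and fades when both arms are almost always significant. Other SDs give the same picture at 4 points with 138/69: active only 40% at SD 20 and 34% at SD 25, against control only 13% and 14%.

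**How much shift the entry rule alone could supply.** Selection acts on the screening VAS, and change is taken from the Day -1 VAS. For a normal score the expected drift from Day -1 to Day 16 is SD × λ × (r1 − r2). Here r1 is the screening-to-baseline correlation, r2 the screening-to-Day 16 correlation, and λ = φ(c)/Φ(c) with c = (50 − mean)/SD. Assume a VAS SD of 18 and a source mean of 40 to 50:
- r1 = r2: the drift is 0, and both arms stay near 2.5%.
- Mean 40 (λ = 0.481), r1 = 0.8, r2 = 0.7: 18 × 0.481 × 0.1 = 0.9 points.
- Mean 45 (λ = 0.630), r1 = 0.8, r2 = 0.6: 18 × 0.630 × 0.2 = 2.3 points.
- Mean 50 (λ = 0.798), r1 = 0.9, r2 = 0.6: 18 × 0.798 × 0.3 = 4.3 points.

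Simulation under these settings gave the same drifts. Significance ranged from 8% to 63% with n = 69 and from 11% to 90% with n = 138.

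**The case against.** The strongest reply is that no efficacy claim rests on these tests. The hypotheses, estimands, mixed model, ANCOVA and between-group tests all compare arms, and section 10 makes testing at Days 45 and 90 conditional on the primary between-arm result. This stands: a shift common to both randomised arms cancels in expectation from the between-arm contrast. A reader might infer that the primary conclusion is biased, but the document does not support that.

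A reader might also infer that entry below 50 guarantees significant within-arm improvement. It does not. Change is measured from the Day -1 value, not from the screening value used for selection, so regression to the mean is removed wholly if it is pure measurement noise and partly if the correlation decays over time. Some decay is plausible, since screening lies about 1 to 6 days before baseline and about 17 to 22 days before Day 16, but the protocol does not quantify it. The remark in section 2.1 that "the degree of symptoms varies over time without any obvious triggers" comes from a paragraph on breathing problems in severely affected non-hospitalised patients. It does not describe VAS scores or the length of good and bad spells. Placebo response and natural course need no selection argument, but their size is not given either.

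Two further limits stand. The arithmetic concerns VAS only: the other endpoints are not selection variables, and the endpoint table lists no dichotomous efficacy endpoint, so no size is shown for McNemar's test. The reverse pattern, control significant and active not, also occurs and must be reported beside the main figure.

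The reply does not justify keeping the tests as written. The protocol prescribes them as hypothesis tests, and section 10.4 expressly defers only sensitivity analyses to the SAP.

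**Conclusion.** The point holds as a possibility, not a certainty. Section 10.4 fixes unadjusted within-arm tests that cannot answer the randomised question, and 2:1 allocation tilts them towards the active arm when a moderate common shift is present.

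With no drug effect, an SD of change of 23.2 and 138/69 completers, a misleading active-only result occurs about 2% of the time at zero shift and 15%, 27% and 37% at 2, 3 and 4 points. With 267/133 it is 39% at 4 points. The reverse occurs 9% to 14% of the time at 2 to 4 points with 138/69, and 10% at 4 points with 267/133. For very large shifts the asymmetry vanishes. All of this rests on an assumed SD and an assumed shift. The damage is confined to supportive claims; the primary comparison and its error rate are unaffected.

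**What to change.** In section 10.4, delete the within-arm paired t, Wilcoxon and McNemar p-values. Report within-arm changes at Days 16, 45 and 90 with confidence intervals, labelled descriptive; for continuous endpoints these can come from the planned model. Add one sentence stating that all efficacy inference rests on the between-arm contrast at each visit.

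The change needs no extra data, visits or patients and reduces the number of tests. Labelling the tests descriptive without removing them would meet part of the concern, but the p-values would still be there to be quoted.
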